1. ABSTRACT

Background: In the U.S., increased intake of fast food and highly processed foods (a “Western-style” diet) has been coincident with the dramatic rise in asthma. Observational studies demonstrate a link between a dietary pattern and asthma morbidity at the level of the individual, and limited trials of counselling for a healthier diet have shown promise in improving asthma health.

Objectives: The objective of the study is to demonstrate the feasibility of a randomized, controlled trial of complete dietary replacement (feeding study) in a population of adults with asthma, and to provide measures of variability in the proposed outcomes (symptoms, lung function, markers of inflammation and oxidative stress) to inform sample size calculation for a larger, definitive trial.

Methods: The study is a feasibility trial of a prudent (high in fruit and vegetables, whole grains, low-fat dairy) versus Western-style (high in processed foods, fast food, sweets) diet intervention in adults with asthma. Eight to twelve adult women (ages 18-55) who meet eligibility criteria will be enrolled. At baseline, demographic information, asthma symptom scores, usual dietary intake, anthropometric measures and DEXA, spirometry, FENO, blood, urine, nasal, and sputum samples will be collected. Participants will then be randomized to either the Western-style diet or a prudent diet. Prior to initiating the diet, they will have assessment of select biologic outcomes (FENO, spirometry, symptom assessment, biomarkers of oxidative stress and inflammation in urine and serum, and nasal swab). After 6 days of the randomized diet, they will repeat these assessments and undergo induced sputum for local (pulmonary) biomarkers of inflammation and oxidative stress. The participants will then have a 4-8 week washout period, and repeat the same order of assessments prior to and after receiving the alternate diet assignment. During each of the 6-day interventions, participants will record asthma-related symptoms via a standardized questionnaire. At the final session, participants will provide feedback on the acceptability and palatability of the dietary interventions and assessments. As this is a feasibility study, we will use results to assess the process and procedures necessary to scale the intervention to a larger study population.

Implications: Study findings will provide insight into feasibility of a larger-scale clinical trial investigating the effect of these diet patterns on adult asthma. We expect to gain insights into the

acceptability of intervention duration, tolerability of study visits and participant flow, and sample size necessary for a larger, definitive clinical trial.

2. OBJECTIVES

The primary objective for this study is to determine the feasibility of a randomized, crossover trial of a Western-style compared to a prudent dietary intervention among Baltimore City adults with asthma. Our secondary objective is to gather preliminary data on markers of systemic and airway inflammation and oxidative stress, lung function, and changes in the microbiome induced by diet to inform sample size for a definitive trial.

3. BACKGROUND

The rising burden of asthma has trended in parallel with dramatic shifts of dietary habits towards a “Western” diet and away from a “prudent” diet (high in fruits, vegetables, whole grains, n3-PUFAs (found in fish, seafood, some plant-based oils), low fat dairy products, and overall antioxidant levels). These trends are particularly relevant to low-income, African American populations who, in addition to their particular vulnerability to asthma, tend to have poorer quality diets, lower in fiber, fruits, and vegetables, and higher in fat and sugar. These correlations have prompted further evaluation, though dietary investigations in asthma have primarily included a focus on individual micronutrients. These include “anti-inflammatory” and antioxidant vitamins (A, C, D, E), minerals (zinc, selenium), flavonoids, and unsaturated fatty acids. While each factor has demonstrated some positive association with improved asthma or wheeze, nearly all have conflicting evidence in the peer-reviewed literature and, disappointingly, randomized trials have shown inconsistent or negative results with single-micronutrient supplementation. The complexity of diet as an exposure variable may be difficult to accomplish by isolating nutrients. For example, while one medium grapefruit contains 200% daily value (DV) of vitamin C, it also contains 70% DV vitamin A, 8% DV calcium, and 16% DV fiber, and has a filling effect that may defer intake of other foods. Unanticipated correlations between nutrients may falsely diminish associations in controlled, statistical analyses, and fail to identify potentially synergistic effects. Because of these issues, there has been increased interest in evaluating whole foods and dietary patterns. To date, nutritional research studies examining dietary patterns have focused heavily on the relationship to other chronic diseases. Whole food intake and dietary patterns have been predictive of multiple disease states, including obesity, cardiovascular disease, and cancer, and there is evidence of an association between healthier, recommended dietary patterns and wellness in these examples. Indeed, evidence exists as to the success of this approach in asthma. A diet rich in antioxidants and low in saturated fats (the Mediterranean diet, similar to the prudent diet but typified by foods endemic to Mediterranean countries, i.e. olive oil, fish, wine) has been proposed as a “respiratory healthy” diet, possibly by attenuating the inflammatory response through high levels of antioxidant intake. Cross-sectional studies suggest better symptom control with adherence to this diet and others similar in composition. Observational work outside of the U.S. demonstrates the positive effects of a “healthy” diet pattern and the negative effects of an “unhealthy” diet pattern on asthma morbidity and respiratory health.

Several small trials of whole food and diet pattern intervention have shown promise. In Australia LG Wood, et al conducted a trial with 137 asthmatic adults who were asked to consume either <1 serving fruit and 2 servings vegetables daily (low antioxidant, LAO) versus 2 servings fruit and 5

[figure not shown]
servings vegetables daily (high antioxidant, HAO). Percent predicted FEV₁ and time to exacerbation were significantly reduced in the LAO compared to the HAO group. The same investigators found that a single high-fat/high-energy meal increased neutrophilic airway inflammation and reduced airway bronchodilator recovery in adult asthmatics. Two small, pilot trials of healthy diets in U.S. populations demonstrate encouraging improvements in asthma outcomes including symptoms, lung function, and serum inflammatory markers. Studies thus far have been limited by either scale-ability (due to duration and therefore cost of studied intervention) or underrepresentation of low-income, African-Americans who have the greatest burden of asthma prevalence and morbidity. Furthermore, the prevalence of adult asthma is 70% higher in females than males, females carry a higher rate of asthma attacks than males, and obesity is a greater risk factor for asthma among adult women compared to adult men. There is a need to define interventions in populations affected the most by asthma, in order to have the greatest impact.

The current study is designed to assess the feasibility of a larger-scale intervention trial comparing a Western-style diet to a prudent diet intervention in an urban population disproportionately affected by asthma. Similarly, because females with obesity represent a high-risk group for asthma incidence and prevalence, and may represent a unique phenotype as compared to males and non-obese individuals, we propose to limit this small pilot to females with obesity.

4. STUDY PROCEDURES

a. Study design summary

Figure 1. Study Design

Experimental Design, BREATHE-Easy Trial

We will conduct a single-blinded (study staff only), randomized crossover pilot trial to evaluate the feasibility of a Western and prudent diet feeding study in Baltimore City adults with asthma (Figure 1). The results from this study will provide data to inform a larger trial evaluating the differential effects of a Western-style (high in processed foods, fast food, sweets) diet and a prudent (high in

fruit and vegetables, whole grains, low-fat dairy) diet on symptoms, lung function, systemic inflammation, and local airway inflammation among adult asthmatics.

Potential study subjects will undergo phone screening prior to invitation for initial clinic visit. Participants will be consented at initial clinic visit, after which they will complete additional eligibility testing (urine pregnancy testing, urinary cotinine measurement, induced sputum collection, and if eligible undergo baseline assessments (demographic information, baseline questionnaire, usual dietary intake evaluation, anthropometric measures, DEXA, spirometry, FeNO, blood, urine, and nasal sample collection). Participants will then be randomized to initiate a Western-style diet or prudent diet and scheduled a date to return for their first assessment (A1) prior to initiating the assigned intervention. FeNO, spirometry, symptoms/questionnaires, and nasal swab, urine, stool/fecal strip, and serum collection will occur at first assessment. Participants will then receive 3 days of meals to take home. Participants will return at day 3 to retrieve the last 3 days of meals (or alternatively, the last 3 days of meals will be delivered to their place of residence), and will return again at day 6 to repeat the assessments at A1 + sputum induction. During each of the Western and prudent intervention diet periods, participants will complete daily questionnaires/diaries on food consumed, symptoms, and other potential exposures that may affect asthma control. Participants will then have an approximately 4-8 week washout period during which they will be instructed to resume their regular diet before continuing with the alternate dietary intervention with mirrored assessments. At the second A2 visit, participants will be asked to answer questions regarding acceptability and tolerability of study schedule and participant flow, and to report comments on study acceptability ad libitum.

i. Recruitment

We will recruit 8-12 obese adult females with asthma, meeting the inclusion and exclusion criteria below. Participants will be recruited using a database of previous study participants in the Center for Childhood Asthma in the Urban Environment (which conducts research in child and adult population) and other Johns Hopkins asthma cohorts currently approved by the Johns Hopkins Institutional Review Board. All potential subjects in this database have consented to having their contact information maintained in a database and to be contacted about participating in research studies.

We will also recruit patients from the Principal Investigator's and Co-Investigator's Pulmonary Clinics who have agreed to be contacted about research studies. In addition, we will recruit potential subjects who are referred from other physicians and have given permission to be contacted. These potential participants will not be approached by research staff or investigators unless they have given permission to their doctors and this permission has been documented in the medical record. All such potential subjects will be given information about the study by their doctor along with study team contact information. They may initiate contact with the study team unless they have given permission to be contacted by a study team member and it is documented in their medical record.

We will also recruit patients at community events and with IRB-approved fliers.

We will also send letters regarding the study to the families of children who have enrolled in our pediatric asthma studies within the Center for Childhood Asthma in the Urban Environment. These families have demonstrated an active interest in research and a high proportion of family members of these children also have asthma. The letter will provide an “opt-out” option where female adult family members may choose not to be contacted by phone. If no “opt-out” letter is returned, we will contact the families to assess interest.

ii. Participant eligibility, baseline visit, and randomization

Participant eligibility is determined by an initial telephone screening call and in an in-person screening visit.

Phone Screening: Potential participants will be asked brief questions on major eligibility criteria (see Section 5), including age, sex, medical history, medications, smoking history and status, food storage and preparation equipment available to the potential participant, and willingness to consume foods planned for the study.

Screening/Baseline exam: All potential participants who pass the phone screen will be invited to consent and complete the in-person screening, which includes an assessment of asthma symptoms via the **Asthma Control Test** (ACT), measurement of **body mass index** (BMI), a **urine cotinine** test and, for women of childbearing potential, a **urine pregnancy test**. Individuals with a negative urine cotinine who are not pregnant will complete initial spirometry and sputum induction.

Spirometry and Induced Sputum Details:

- 1) **Spirometry** will be performed according to American Thoracic Society guidelines using a KOKO (Pulmonary Data Services, Inc., Louisville, CO) pneumotachometer to obtain FEV₁, FVC, FEF₂₅₋₇₅, and PEF. After spirometry is obtained, participants will be administered 2 puffs of albuterol via a spacer. After 15-45 minutes, spirometry will be repeated. With each spirometry session, 3 sets of FEV₁ values will be obtained. The highest FEV₁ measurement post albuterol administration will be used to determine eligibility for induced sputum (must be >60% of predicted value based on standard reference equations adjusted for age, race, gender, and height).
- 2) **Sputum induction:** Participants will be instructed through an induced sputum procedure via hypertonic saline nebulization. Sputum inductions and processing will be performed following published protocols. Briefly, after baseline spirometry, an ultrasonic nebulizer will be used to deliver hypertonic saline for at most a total of 20 minutes. The subject will be asked to expectorate sputum into a specimen cup placed on ice. Lung function will be monitored to ensure participant safety. If there is a fall in FEV₁ of $\geq 20\%$ compared baseline FEV₁ prior to sputum induction at any point or if the patient is unwilling or unable to continue, sputum induction will be terminated and albuterol administered as needed.

Those who are able to successfully produce an adequate sputum sample will be enrolled in the full trial and asked to complete the baseline evaluation on the same day.

The baseline evaluation will include the following:

- 1) **Collection of demographic information**, including name, address, date of birth, and medical history
- 2) **Baseline questionnaire**, including questions on common exposures known or hypothesized to exacerbate asthma (i.e. cleaning products, home environment, etc).
- 3) **Symptom report** via questionnaires. These include the Asthma Quality of Life Questionnaire (AQLQ), Asthma Symptom Utility Index (ASUI), and Asthma Control Test (ACT). The AQLQ has been validated for individuals 15 and older and is designed to measure daily impact of asthma in patients' lives. The ASUI is a validated 2-week recall questionnaire that addresses issues of asthma control weighted by impact on functional status. The ACT is a validated 4-week recall of symptoms and functioning.
- 4) **Other questionnaires** aimed at assessing self-efficacy in disease management, including the validated PROMIS-29 and EQ-5D-5L.
- 5) **Instruction for evaluation of usual diet** via a 3-day food diary, to be completed at home over the ensuing 3 days.
- 6) **Assessment of daily caloric** needs by a registered dietitian, on which to base calories provided during 6-day feeding intervention.
- 7) **Dual Energy X-ray Absorptiometry (DEXA) Scan** at the Johns Hopkins Hospital Broadway Adult Outpatient CRU.
- 8) **Anthropometric measures** of height, weight, waist circumference, chest circumference, and neck circumference
- 9) **Fractional exhaled nitric oxide (FeNO) measurement:** Exhaled nitric oxide is a known marker of pulmonary inflammation and will provide a means of assessing pulmonary oxidative stress and inflammation. Measurement of exhaled nitric oxide will be obtained according to ATS guidelines and prior to lung function whenever possible. Nitric oxide concentrations will be measured using a chemiluminescent analyzer (NIOX Mino, Aerocrine, Sweden). This equipment is FDA-approved for clinical use in asthma management.
- 10) **Serum collection:** Serum will be collected via phlebotomy, a routine clinical procedure performed by drawing blood from a vein in the forearm, in order to investigate serum biomarkers indicating inflammation and oxidative stress, such as IL-5, IL-13, RANTES, superoxide anion, and lipid peroxides. Any excess serum will be stored for future analyses.
- 11) **Urine collection:** Prior to enrollment, all participants will submit a urine sample for pregnancy testing, and urine will also be collected for analysis at each assessment visit. Urine biomarkers, including LTE4 and F-isoprostane, will be measured to assess oxidative stress and inflammation. We will also measure other markers of inflammation/chemical exposure that may affect asthma control. Any excess urine will be stored for future analyses.
- 12) **Nasal swab collection:** Nasal swab (and optionally, oropharyngeal and skin swab) collection will occur at each assessment visit, before and after each dietary intervention, to obtain a sample for cellular examination. Analysis of biomarkers in nasal specimens will include (1) cell count and differential, (2) cytokines, (3) chemokines, and other markers of inflammation, (4) microbial assessment.

Randomization: Randomization will occur within approximately one to two weeks of enrollment. Participants will be randomized using a computerized random assignment table with permuted blocks. Participants will be aware of their assignment as the study cannot be blinded.

iii. Intervention

Participants will be provided with all meals for 6 days through the Nutrition Core at the ICTR. Meals will be calorically balanced such that the “prudent” versus “Western-style” intervention will contain similar caloric counts.

Participants will be instructed not to consume meals or snacks outside of those provided and will be asked to visit the research clinic at most twice to pick up their meals: once at initial assessment, and mid-way through the intervention period, they may either return to the clinic to pick up the remainder of their meals or their meals will be delivered to their home. For each day of this controlled feeding, participants will also complete a **daily diary**. The daily diary asks about study foods not eaten, non-study foods eaten, and beverages consumed over the past day. Participants will also report **daily symptom assessment** with validated symptom scales and rescue inhaler use daily during the 6-day dietary intervention, as well as exposures that may affect asthma control.

A washout period of approximately 4-8 weeks separates each intervention period; the washout period allows ad libitum food intake.

Description of Diets:

Energy values and macronutrient distribution (as percent of kilocalories) will be similar for the prudent and Western diet with a goal of 35-37% Fat, 45-47% Carbohydrate, and 16-18% Protein. Differences between the diets are defined in the table below.

Nutrient or Food Pattern	Western Diet	Prudent Diet
Saturated fat (% of kcals)	≥10	<8
Omega-6:Omega-3 ratio	≥13:1	≤5:1
Whole grains (% of grain servings)	0	100
Fruit (servings/day)	≤1	≥3
Vegetable, not potato (servings/day)	≤1	≥3
Nuts (1 oz. serving/day)	0	≥1
Fish (3 ounce serving 4/6 days)	0	2
Processed meat (ounces/day)	≥3	0
Sweets (30-125 gram serving/day)	≥1	0
Sugar sweetened beverages (fluid ounces/day)	≥8	0

Food Production and Distribution:

Meals will be prepared and distributed in the research kitchen of the Nutrition Core at the ICTR. The research kitchen is inspected annually by the Baltimore City Health Department. Managers and staff of the ICTR research kitchen are certified through ServeSafe. Participants will be instructed in food safety.

Promotion of Adherence: Efforts to promote adherence begin at the earliest stages of the study. During the phone and in-person screenings, participants are repeatedly provided with information about key features of the study. During the phone screening, participants will complete the Diet Screening Form, which includes a detailed list of foods provided. Individuals must be willing to eat

each of these foods; otherwise, they are excluded. Key contacts with nutrition staff include an in-person evaluation by a dietitian. The intent of these efforts is to identify and exclude, prior to randomization, participants who are unwilling or unable to comply with the feeding protocol.

Efforts to promote adherence center on making the foods palatable and convenient to the participant lifestyles; maintaining easy access to staff; and providing available, daily, supportive contacts. Acceptance of the controlled feeding protocol is increased by allowing participants to consume pre-approved selected beverages, as well as an unlimited amount of water and artificially sweetened soft drinks.

Assessment of Adherence

Adherence assessment includes both self-reported and objective measures. The subjective measures are used to determine suitability for randomization and subsequently to counsel participants and promote adherence during the trial. Self-reported measures are obtained from information provided on a daily diary and from subjective judgment by clinic personnel. Each day, an overall compliance score (0=compliant; 1, 2, or 3 for various degrees of non-compliance) is calculated based on staff observation and information from the daily diary. Adherence will also be assessed at each post-intervention assessment via objective measures, including serum biomarkers (lipids, carotenoids, and free fatty acids), and on-site meal consumption of the first meals within each intervention. Comparison pre- and post-intervention will provide objective measures of adherence to provided intervention.

iv. Assessments

Assessments will include the following (refer to Figure 1):

Assessment 1 (before the dietary intervention period)

- 1) Spirometry:** Spirometry will be performed according to ATS guidelines to obtain FEV₁, FVC, FEF₂₅₋₇₅, and PEF. After spirometry is obtained, participants will be administered 2 puffs of albuterol via a spacer. After 15-45 minutes, spirometry will be repeated. At each examination, 3 sets of FEV₁ values will be obtained, and the highest FEV₁ measurement will be used as the baseline measurement for FEV₁ recovery.
- 2) Fractional exhaled nitric oxide (FeNO) measurement:** Exhaled nitric oxide is a known marker of pulmonary inflammation and will provide a means of assessing pulmonary oxidative stress and inflammation. Measurement of exhaled nitric oxide will be obtained according to ATS guidelines and prior to lung function whenever possible. Nitric oxide concentrations will be measured using a chemiluminescent analyzer (NIOX Mino, Aerocrine, Sweden). This equipment is FDA-approved for clinical use in asthma management.
- 3) Serum collection:** Serum will be collected via phlebotomy, a routine clinical procedure performed by drawing blood from a vein in the forearm, in order to investigate serum biomarkers indicating inflammation and oxidative stress. Any excess serum will be stored for future analyses.
- 4) Urine collection:** Prior to enrollment, all participants will submit a urine sample for pregnancy testing, and urine will also be collected for analysis at each assessment visit. Urine biomarkers, including LTE₄ and F-isoprostane, will be measured to assess oxidative stress and inflammation.

We will also measure other markers of inflammation/chemical exposure that may affect asthma control. Any excess urine will be stored for future analyses.

- 5) **Stool/Fecal strip sample:** One sample will be collected to analyze gut microbiome at baseline and during each follow-up visit. Sample will be stored at -80°C until further analysis of gut microbiome.
- 6) **Symptom report** via questionnaires including the Asthma Quality of Life Questionnaire (AQLQ), Asthma Symptom Utility Index (ASUI), and the Asthma Control Test (ACT). The AQLQ has been validated for individuals 15 and older and is designed to measure daily impact of asthma in patients' lives. The ASUI is a validated 2-week recall questionnaire that addresses issues of asthma control weighted by impact on functional status. Participants will also complete daily symptom diaries during the 6 days of intervention. The ACT is a validated 4-week recall of symptoms and functioning.
- 7) **Nasal swab collection:** Nasal swab (and optionally, oropharyngeal and skin swab) collection will occur at each assessment visit, before and after each dietary intervention, to obtain a sample for cellular examination. Analysis of biomarkers in nasal specimens will include (1) cell count and differential, (2) cytokines, (3) chemokines, and other markers of inflammation, (4) microbial assessment.

Daily Diaries:

During the course of each feeding period, participants will complete daily diaries (questions and format supplied) to document data such as adherence to the diet, use of cleaning products, symptoms and albuterol use. Participants will be contacted daily with reminders to complete the diaries and to allow for any participant questions or concerns. Telephone calls or text messages will be used for this purpose.

Assessment 2 (after the dietary intervention period) will include all of the above assessments, plus:

- 8) **Sputum induction:** Participants will be instructed through an induced sputum procedure via hypertonic saline nebulization. Sputum inductions and processing will be performed following published protocols. Briefly, after baseline spirometry, an ultrasonic nebulizer will be used to deliver hypertonic saline for at most a total of 20 minutes. The subject will be asked to expectorate sputum into a specimen cup placed on ice. Lung function will be monitored to ensure participant safety. If there is a fall in FEV₁ of $\geq 20\%$ compared baseline FEV₁ prior to sputum induction at any point or if the patient is unwilling or unable to continue, sputum induction will be terminated and albuterol administered as needed.
- 9) **Feedback session:** We will solicit feedback on acceptability of intervention and satisfaction with study structure, including study instruments administered to optimize participant experience and retention for an anticipated, larger-scale trial.

b. Study duration and number of study visits required of research participants

Each study participant will be enrolled for a maximum of approximately 16 weeks, and with rolling enrollment we anticipate completion of all study visits within 1 year. Each research participant will be required to attend a baseline clinic visit and four assessment clinic visits. In addition, during each of the Western and prudent intervention periods, the participants will be required to pick up their meals at most twice: once at initial assessment, and mid-way through the intervention period, they

may either return to the clinic to pick up the remainder of their meals or their meals will be delivered to their home. In total, each research participant will be required to make five to seven study-related visits.

c. Blinding, including justification for blinding or not blinding the trial, if applicable.

It is not possible to blind participants to this protocol, as they will be aware which diet they have been assigned. Participants will be randomized using a computerized random assignment table with permuted blocks to receive either the “Western” or “prudent” diet first, and they will receive the alternate diet after the washout period. We will blind investigators and all study staff outside of the nutrition CRU staff to diet assignment.

d. Justification of why participants will not receive routine care or will have current therapy stopped.

All patients enrolled in this study will continue to have their usual care for asthma as determined by their primary care provider or their usual asthma caregiver. The study protocol will not interfere with participants receiving their previous routine medical care. A copy of all complete blood count results along with a copy of all pulmonary function test results obtained during their visits will be given to the participants at the end of the study accompanied by a letter for their PCP.

e. Justification for inclusion of a placebo or non-treatment group.

Each participant will receive both dietary interventions, the “Western” diet and the “prudent” diet.

f. Definition of treatment failure or participant removal criteria.

We do not anticipate that participants will experience any significant side effects from ingestion of the study diets.

At any time, the subject’s participation will stop if he/she requests not to proceed with the study or at the determination of the Principal Investigator.

g. Description of what happens to participants receiving therapy when study ends or if a participant’s participation in the study ends prematurely.

If a participant’s participation in the study ends prematurely, no additional dietary measures will be taken. Participants will resume their typical diet once the study concludes or when the participant exits the study.

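### Baseline FeNO is scheduled after spirometry, albuterol and hypertonic saline, against the protocol's own FeNO-first rule: a minor conflict that is cheap to fix

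*Combined protocol and SAP*

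**What the plan says.** **Rule.** Item 9 of the baseline evaluation (Section 4.a.ii) says FeNO is to be "obtained according to ATS guidelines and prior to lung function whenever possible".

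**Screening sequence.** The same section says: "Individuals with a negative urine cotinine who are not pregnant will complete initial spirometry and sputum induction". Within that step, "After spirometry is obtained, participants will be administered 2 puffs of albuterol via a spacer", and spirometry is repeated 15-45 minutes later. For the induction that follows, "an ultrasonic nebulizer will be used to deliver hypertonic saline for at most a total of 20 minutes". Women who give an adequate sample are "enrolled in the full trial and asked to complete the baseline evaluation on the same day". The design summary in Section 4.a agrees: induced sputum is part of eligibility testing, and FeNO is among the assessments made once a woman is found eligible.

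**Assessment visits.** Section 4.a.iv repeats the FeNO-first sentence at A1, as item 2 after spirometry with albuterol as item 1. The design summary names FeNO first: "FeNO, spirometry, symptoms/questionnaires, and nasal swab, urine, stool/fecal strip, and serum collection will occur at first assessment". A2 repeats the A1 assessments and adds sputum induction, listed after them.

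**Where FeNO is measured.** Section 8 places FeNO at the four assessment visits and does not mention baseline. The abstract, Section 4.a and Section 4.a.ii all include it at baseline.

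**Analysis.** Section 7.c summarises FeNO at each time point and compares post-diet levels between diets by paired t-test. It also plans ICCs from mixed models for target biomarkers, which it does not name.

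**The concern.** The protocol states a preferred order for FeNO and then sets out a screening day on which that order cannot be kept. If the order matters, as the rule implies, baseline FeNO is taken under different conditions from A1 and A2. Five FeNO readings per woman would then not form one comparable series.

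This deserves attention in a pilot because variability estimates are one of its stated products: they are meant to inform the sample size of a larger trial. With 8-12 women, a procedural difference between visits is hard to separate from real within-woman variation afterwards, and it cannot be separated at all if the order was not recorded.

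**Working it through.** The plan states no FeNO variance, effect size or power figure, so there is nothing to reproduce. The main check is on the text.

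**Step 1. Sequence on the baseline day (Sections 4.a and 4.a.ii).**
1. Cotinine and pregnancy tests
2. Spirometry
3. Albuterol
4. Repeat spirometry at 15-45 minutes
5. Hypertonic saline induction, at most 20 minutes
6. Enrolment if the sputum is adequate
7. Baseline evaluation the same day, with FeNO as item 9

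FeNO is in step 7 and lung function in steps 2 and 4. Moving FeNO to the top of the baseline evaluation would not help, because the whole evaluation follows step 5.

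**Step 2. Is baseline FeNO intended?** The abstract, Section 4.a and Section 4.a.ii say yes; Section 8 omits it. Section 8 also gives phlebotomy and nasal swabs at the four assessment visits only, although both are on the baseline list. That looks like loose drafting in Section 8, but the text does not settle it.

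**Step 3. Which analyses use which reading (Section 7.c)?**

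| Analysis | Baseline | A1 | A2 |
|---|---|---|---|
| Summary at each time point | yes, if measured | yes | yes |
| Paired t-test between diets | no | no | yes |
| ICC / temporal variability | not stated | not stated | not stated |

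**Step 4. Possible effect on an ICC (every input assumed).** Work on the log scale, with between-woman SD sb = 0.5, within-woman SD sw = 0.15 or 0.25, and a reading lowered by 5-20% at baseline only, so d = -ln(1 - shift) = 0.051 to 0.223. Suppose baseline is one of five visits in a model with no visit term. The within-woman variance then gains d²/5:

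ICC = sb² / (sb² + sw² + d²/5)

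- sw = 0.15: with no shift, 0.25/0.2725 = 0.917. With the shift, 0.916 (5%) to 0.885 (20%).
- sw = 0.25: with no shift, 0.25/0.3125 = 0.800. With the shift, 0.799 (5%) to 0.775 (20%).

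This holds sb² fixed. The usual one-way estimator would also lower it by d²/25. At d = 0.223 that is 0.002, giving 0.248/(0.248 + 0.0225 + 0.010) = 0.884 in place of 0.885. A visit term in the model would absorb a shift common to all women.

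**Step 5. What a varying order at A2 would do (every input assumed).** If a share p of A2 readings is taken out of order, independently between a woman's two A2 visits:

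SD of paired difference = √(2sw² + 2p(1-p)d²)

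Take a 10% shift (d = 0.105) and p = 0.25. The added term is 2 × 0.1875 × 0.0111 = 0.0042.

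- sw = 0.15: SD rises from √0.045 = 0.212 to √0.0492 = 0.222, or 4.5%. The implied N for a later trial rises by about 9%.
- sw = 0.25: SD rises from √0.125 = 0.354 to √0.1292 = 0.359, or 1.7%. N rises by about 3%.

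Across shifts of 5-20% and p of 0.1-0.5, N rises by 0.4% to 55%. The top end needs half the A2 readings out of order and a 20% shift. With one fixed order (p = 0 or 1) the added term is zero, because a shift common to both A2 visits cancels.

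**The case against.** The strongest reply is that nothing the trial will conclude about diet depends on baseline FeNO. The t-test uses A2 values only, there is no change-from-baseline analysis, and A1, taken on a later day before the diet starts, gives a separate pre-diet reading. The primary outcome is qualitative and FeNO is one of many secondary markers. All of that stands, and it is why the point is minor.

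It can also be said that the rule carries its own exception, "prior to lung function whenever possible", so no rule is broken at baseline. That is only partly right. The exception suits an occasional practical obstacle; here the written sequence makes it apply to every enrolled woman.

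A reader might infer more than the documents support, in three ways:

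- **That the order at A1 and A2 is left open.** The numbering in Section 4.a.iv puts spirometry first, but a numbered list is not a visit schedule. FeNO-first is the stated default there, the design summary names FeNO first, and nothing at those visits prevents it.
- **That the diet comparison is contaminated.** Baseline and A1 readings do not enter it. Only an order that differed between a woman's two A2 visits would add noise, and only one that differed by diet would bias it. The documents give no reason to expect either.
- **That a definite amount of error is added.** The documents never say that spirometry, albuterol or saline changes FeNO, or by how much. The concern rests on the protocol's own ordering preference. FeNO is not named among the ICC biomarkers either.

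**Conclusion.** The conflict at baseline is real and follows from the text alone: Section 4.a.ii asks for FeNO before lung function and schedules it after lung function, albuterol and saline. Section 8 adds an inconsistency about whether it is measured at baseline at all.

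The reach is narrow: the baseline FeNO summary, its comparability with A1 and A2, and any ICC that uses both FeNO and that visit. The size cannot be taken from the documents. The ICC changes in the working (0.917 to 0.885 at most for sw = 0.15, 0.800 to 0.775 for sw = 0.25) depend on assumed SDs, an assumed shift, and a model without a visit term. The A2 figures describe a departure that the plan does not predict; they show only why the order should be recorded. This is a cheap improvement of minor weight.

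**What to change.** 1. Reconcile Sections 4.a, 4.a.ii, 4.a.iv and 8 on whether FeNO is measured at baseline and at what point in the visit.
2. If baseline FeNO is kept, take it at the in-person screening after consent and before the first spirometry. The rest of the screening sequence stays as written.
3. In Section 4.a.iv, list FeNO ahead of spirometry, so that the list agrees with the rule and with the design summary, and use the same order at all visits.
4. Record the order (and time) of FeNO and spirometry at each visit. State in Section 7.c that out-of-order readings will be flagged and examined in a sensitivity analysis.
5. In Section 7.c, say whether FeNO is one of the ICC biomarkers and which visits contribute.

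The cost is a few FeNO readings in women who then fail screening, plus one field on the visit form. It should be done before enrolment, since an order that was not recorded cannot be recovered later.
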